7.2 Standard assessment procedures

7.2.1 Nutritional assessment

At the time of the patient's admission, a dietary assessment is carried out by the dietitian in accordance with the recommendations issued by the French Association of Dieticians-Nutritionists (AFDN) and the HAS. The dietitian collects all the data required to detect malnutrition, such as weight, height, BMI, albumin levels, as well as grip strength and walking speed (carried out by the care assistant and the physiotherapist or the EAPA). The dietitian also looks for possible barriers to feeding such as dental condition, swallowing problems or digestive discomfort.

The doctor looks for various pathologies impacting on digestive absorption such as short stool syndromes, gastrectomies, pancreatic insufficiency etc. He also looks for aggressive factors

such as cancers, chronic progressive diseases, infections etc. He also looks for factors of aggression such as cancers, chronic progressive diseases, infections etc.

All of these data make it possible to estimate the theoretical nutritional needs of the patient and to adapt the nutritional management. A follow-up of the ingestions is carried out by the dietician in collaboration with the nurses' aides.

7.2.2 Anthropometric measurements

On admission, the ward's nurses and orderlies measure the patient's weight and height. When the patient can maintain an upright position, a conventional scale and a measuring rod are used for the measurements. If the patient cannot maintain this position, a weighing chair and a laser meter are used.

In order to assess weight loss prior to hospitalisation, the previous weight is sought in a hospital report or other recent medical document. Contact with the attending physician is also made in order to obtain information about the patient's weight monitoring. When this information is not available, the previous weight given by the patient is collected.

7.2.3 Biological measurements

On admission, a biological sample is usually taken from patients at risk of undernutrition in order to measure pre-albumin, albumin and C-reactive protein (CRP). These elements make it possible to determine the severity of undernutrition when it is present, according to the diagnostic criteria of the HAS.

7.2.4 Measures of muscle function

Handgrip force measurement ("Handgrip ")

The grip strength is assessed with the Jamar® hydraulic dynamometer by the caregiver.

The patient is in a seated position, on a chair with a backrest, with the feet on the floor. The device is placed in the patient's hand. The patient is instructed to squeeze the dynamometer as hard as possible.

The measurement is taken on the dominant side of the patient. The homolateral shoulder is in adduction (elbow to body), without extension or flexion and in neutral rotation. The elbow is bent to 90° and in neutral pronation. The wrist is in neutral position. Three trials will be carried out, and the best value (in Kg) of the different trials is retained (see measurement procedure in **Appendix 2**).

Gait speed measurement

Walking speed (m/s) is measured on a 4-metre course in a corridor by the EAPA or physiotherapist. The course is marked out on the ground. There are also 1 metre run-up and deceleration zones. The patient is instructed to walk the course at a normal speed and not to complete the distance as quickly as possible. The course is completed 3 times and the best time (in seconds) is recorded (see procedure in [Annex 3](#)).

8 Evaluation procedure added by the research

8.1 Mini-Nutritional Assessment Short Version (MNA-SF) score

The MNA-SF is a validated nutritional risk screening tool that can be applied by health professionals (see [Appendix 4](#)). It was developed by Rubenstein (23) based on the MNA. Completed in less than five minutes, it can identify a decrease in food intake, acute pathology or stress and a drop in BMI. It also includes two questions related to the frailty of the elderly, mobility and neuropsychological problems (dementia, depression).

The MNA-SF classifies people as "undernourished" with a score between 0 and 7 points, "at risk of undernutrition" with a score between 8 and 11 points and "satisfactory nutritional status" with a score between 12 and 14 points. Patients considered "undernourished" and "at risk of undernutrition" should have their nutritional status assessed.

8.2 Diagnosis of undernutrition according to the GLIM criteria

The diagnosis of undernutrition will also be carried out in the framework of this research according to the GLIM criteria. It will be based on the search for at least 1 phenotypic criterion and 1 etiological criterion. Severe undernutrition will be based solely on phenotypic criteria. See detailed description in section 10.1.

This diagnosis according to the GLIM definition will be made by one of the investigators not involved in the management of the patient. The patient's team will be blinded to these results so as not to influence the management of the patient.

8.3 Impedance measurement bio-electrical

Bioelectrical impedance measurement is carried out in the patient's room using the Z-Metrix impedance meter from Bioparhom. The test is carried out when the patient is admitted to the ward.

The patient is positioned in the supine position, inclined at 30 degrees. The patient must rest for at least 15 minutes before the measurement. Four electrodes are placed:

- On the flat of the back of the hand;

- In the wrist at the level of the head of the ulna, in the intertendinous hollow;
- At the ankle, above the lateral malleolus ;
- Above the previous electrode, spaced about 4 fingerbreadths apart.

This non-invasive test quantifies muscle, lean and fat mass as well as bone and water mass. Values are expressed in kilograms and as a percentage of body weight (see measurement procedure in [**Appendix 5**](#)).

The following clues will be collected:

- Muscle mass index (in kg/m^2);
- Non-fat mass index (in kg/m^2).

9 Conduct of the research

9.1 Pre-inclusion visit

9.1.1 Checking inclusion and non-inclusion criteria

When a patient is admitted to short-stay and follow-up care and rehabilitation in diabetes-obesity, pneumology, oncology and gastro-nutrition, one of the investigators checks the presence of the inclusion criteria and the absence of the non-inclusion criteria in the institution's computerised medical record.

9.1.2 Sampling of the population

A potential of 94 patients per month eligible for this study are admitted in the short stay and follow-up care and rehabilitation of diabetology-obesity, pneumology, oncology and gastro-nutrition. We anticipate a maximum inclusion of 13 patients per month for logistical reasons. In order to obtain a representative sample of this patient population in the study, we will sample the patient population on admission , if they meet the eligibility criteria and before the patient is informed and consents are obtained. The patient will be randomly assigned to either the eligible or the ineligible group of the study. Patients in the ineligible group will therefore not be included in the study, but the number of such patients will be collected.

Patients will be sampled via a centralised randomisation system available via the internet, according to a pre-determined randomisation list. The randomisation list will be scheduled in advance by the study statistician. The sampling will be stratified on the care service, and unbalanced using random blocks in order to obtain a number of eligible patients of 15 patients per month (in order to take into account possible refusals of participation). Only the hospital research coordinator will know the randomisation list.

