10.1 Prevalence of undernutrition

Undernutrition is defined according to the diagnostic methods of the HAS and GLIM:

	Phenotypic criteria			Etiological criteria	
	Weight loss (%)	Low BMI (kg/m ²)	Reduction in muscle mass	Reduction in food intake or absorption	Inflammatory situation
GLIM	> 5% in the last 6 months or > 10% beyond 6 months	< 20	Reduction assessed by a validated measurement technique*.	≤ 50% of food intake > 1 week or any reduction > 2 weeks, or any gastrointestinal conditions or symptoms impacting assimilation or absorption	Acute or certain chronic or malignant conditions
HAS	≥ 5% in 1 month or ≥ 10% in 6 months or loss ≥ 10% from usual weight before onset of disease	< 18,5	Quantified Reduction** (QR)	Same as	Same as

For the GLIM and HAS diagnostic method, the diagnosis of undernutrition is positive if an etiological criterion and a phenotypic criterion are present. The assessment of undernutrition according to GLIM will be preceded by a MNA-SF ([Appendix 4](#)). The methods for measuring the reduction in muscle mass are described in section "**7.2.4. Measurement of muscle function**".

Among patients with undernutrition, severe undernutrition is defined by :

	Moderate undernutrition	Severe undernutrition
GLIM	
 • BMI < 20 kg/m² • Weight loss of 5-10% in the last 6 months or 10-20% beyond 6 months • Mild to moderate reduction in muscle mass 	
 • BMI < 18.5 kg/m² • Weight loss of >10% in the last 6 months or >20% beyond 6 months • Severe reduction in muscle mass
HAS	
 • 17 < BMI < 18.5 kg/m² • Weight loss ≥ 5% in 1 month or ≥ 10% in 6 months or loss ≥ 10% from usual weight before onset of disease • Measurement of albumin by immuno-electrometry or immunoturbidimetry > 30 g/L and < 35 g/L. 	
 • BMI < 17 kg/m² • Weight loss ≥ 10% in 1 month or ≥ 15% in 6 months or loss ≥ 15% from usual weight before onset of disease • Measurement of albumin by immuno-electrodelemetry or immunoturbidimetry < 30 g/L

The prevalence of undernutrition is defined as the proportion of patients with moderate and/or severe undernutrition among the patients included in the study.

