13.2 Expected benefits for the patient

This study could highlight a difference in the prevalence of undernutrition according to the definitions and tools used. The results of this study will not provide direct benefits for the patient, but could allow the clinician to be more vigilant if undernutrition is underestimated, according to the criteria used in France. The benefit would then be a broader screening of undernutrition and would allow the adaptation of the patient's nutritional and rehabilitation management.

14 Feasibility

Taking into account the inclusion and non-inclusion criteria, possible refusals of patients to participate in the research, potential exclusions and recruitment experience, we estimate a minimum recruitment capacity of 50% of patients admitted to short-stay and follow-up and rehabilitation care for diabetes-obesity, pneumology, oncology and gastro-nutrition, i.e. 47 patients per month, with a monthly recruitment target of 13 patients over 20 months.

In addition, screening for undernutrition is usually carried out on all patients admitted to these wards within our establishment. Dieticians, nursing assistants, nurses and doctors are therefore trained and used to carrying out this screening. Bioelectrical impedance measurement by dieticians is already performed on some patients, and takes no more than 15 minutes. The addition of this test to the research framework is therefore feasible.

In addition, the teams have experience in clinical research, as they are already involved in other research projects as promoters and investigating centres. The medical and rehabilitation teams are involved in other ongoing research projects (<https://clinicaltrials.gov/ct2/show/NCT02881814><https://clinicaltrials.gov/ct2/show/NCT02474797> and <https://clinicaltrials.gov/ct2/show/NCT04373811>).

15 Ethical and regulatory aspects

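### The draw is stratified by care service, but no sampling fraction per service is given and the prevalence analysis ignores the stratum, so the two reported prevalences may shift modestly; the HAS–GLIM comparison is hardly affected.

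*Combined protocol and SAP*

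**What the plan says.** Section 9.1.2 states the aim of the sampling: "In order to obtain a representative sample of this patient population in the study". It puts the source at 94 patients a month and limits inclusion: "We anticipate a maximum inclusion of 13 patients per month for logistical reasons". On the design it says: "The sampling will be stratified on the care service, and unbalanced using random blocks in order to obtain a number of eligible patients of 15". That figure is a monthly total, the margin over 13 being for refusals. No fraction or quota is given for any single service.

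The order of steps matters. Under 9.1.1 the criteria are checked in the medical record. Under 9.1.2 the draw is made among patients who meet them, before information and consent. On those not drawn: "Patients in the ineligible group will therefore not be included in the study, but the number of such patients will be collected". A breakdown of that number by service is not mentioned. Section 9.2 records the service of each included patient.

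Section 10.1 defines prevalence as the "proportion of patients with moderate and/or severe undernutrition among the patients included in the study". Section 11.3 compares the two prevalences by McNemar. Nothing in section 11 uses service as a weight, stratum or subgroup.

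**The concern.** A stratified random draw with one common fraction makes the drawn patients representative by service. It does not by itself make the included patients representative, because refusal comes after the draw. It also does not make the drawn patients representative if the fraction differs between services, and the text leaves that open.

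Diabetology-obesity, oncology, pneumology and gastro-nutrition can be expected to differ in undernutrition. A crude proportion then depends partly on which services supplied the patients. The primary outcome in 4.1 is the prevalence under each definition in patients hospitalised in these services, so the two reported percentages are at stake. A shift of this kind is a bias that the planned confidence intervals do not cover.

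**Working it through.** **The plan's own figures.** 1128 / 12 = 94 admissions under 70 a month (5.3). 13 × 20 = 260 included. 15 / 94 = 16.0% drawn overall. 13 / 15 = 86.7% of those drawn are expected to be included. The 95% CI half-width at n = 260 is 1.96 × √(0.34 × 0.66 / 260) = 5.8 points at 34%, and 1.96 × √(0.49 × 0.51 / 260) = 6.1 points at 49%.

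**Formula.** With w the service's share of eligible patients, r its inclusion rate among those drawn and p its prevalence, under one common sampling fraction:

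- target prevalence = Σ w·p
- crude prevalence = Σ w·r·p / Σ w·r

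If r is the same in every service, the two are equal and the shift is zero.

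**Assumption set 1** (mine; the documents give no values by service). Order: diabetology-obesity, pneumology, oncology, gastro-nutrition. Shares 30/25/25/20%; HAS 10/35/50/45%; GLIM 22/47/68/65%.

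- Target HAS = 0.030 + 0.0875 + 0.125 + 0.090 = 33.3%
- Target GLIM = 0.066 + 0.1175 + 0.170 + 0.130 = 48.4%
- Difference 15.1 points, close to the 34%, 49% and 15 points in 11.1

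| Inclusion of those drawn | Mean inclusion | Crude HAS (shift) | Crude GLIM (shift) | Difference |
|---|---|---|---|---|
| equal in all services | any | 33.3% (0) | 48.4% (0) | 15.1 |
| 95/90/80/80% | 87.0% | 0.27925 / 0.870 = 32.1% (−1.2) | 0.40845 / 0.870 = 46.9% (−1.4) | 14.9 |
| 75/85/95/95% | 86.5% | 0.301125 / 0.865 = 34.8% (+1.6) | 0.434375 / 0.865 = 50.2% (+1.9) | 15.4 |
| equal numbers per service | – | 35.0% (+1.8) | 50.5% (+2.2) | 15.5 |

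**Assumption set 2, to bracket the extremes.** HAS 10/30/46/50% and GLIM 20/48/62/66%. With four equal services these average 34% and 49%.

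- *Acceptance 95/90/80/75%:* crude 32.6% and 47.4%, difference 14.9.
- *Whole 15-to-13 loss in one service* (3.75 drawn a month in each, 2 lost in one): crude HAS 31.5% to 37.7%, crude GLIM 46.4% to 53.5%. Shifts run from about −2.6 to +4.5 points; the difference is 14.5 to 15.8.
- *Equal quotas with unequal admissions:* crude stays at 34% and 49%. The target is 28.2% and 42.3% if admissions are 40/25/20/15%, or 39.0% and 54.5% if they are 15/20/25/40%. Shifts are 5 to 7 points; the difference is 15.0 against 14.1 or 15.5.

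**Precision.** Using the stratum can also narrow the interval. Under set 1 with proportional inclusion, the variance falls from P(1−P) to Σ w·p(1−p):

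- HAS: 0.1959 against 0.2219; 1 − √(0.1959 / 0.2219) = about 6% narrower.
- GLIM: 0.2137 against 0.2497; 1 − √(0.2137 / 0.2497) = about 7.5% narrower.

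**The case against.** The strongest reply is that the primary question is a within-patient comparison. Each patient is classified by both definitions, so a change in service mix moves both prevalences together and nearly cancels in the difference. This stands: the difference moves by 0.3 point at planned inclusion and by at most 0.9 point in the extreme cases, against a 15-point target. McNemar is valid for the included patients.

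A second reply is that nothing in the documents shows unequal inclusion. This also stands. One fraction for all services would be self-weighting, and *unbalanced* in 9.1.2 most naturally describes the ratio of drawn to not drawn patients, not different fractions between services. The shifts of 1 to 2 points are also well inside a half-width of about 6 points.

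Two stronger readings are tempting and should not be drawn.

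- *Half of the drawn patients may be lost.* Section 14 says "we estimate a minimum recruitment capacity of 50% of patients admitted". That is a share of admissions (47 of 94), given as a minimum capacity after criteria, refusals and exclusions. Patients who cannot have impedance or who have limited care are normally removed before the draw. Inclusion of 60/50/35/40% or 40/50/60/60% of those drawn would give shifts of 2.6 to 3.9 points under set 1. But these rates average 47% and 51.5%; of 15 × 20 = 300 drawn they leave about 142 or 155 patients, which contradicts the planned 260.
- *The counts needed for a correction are already collected.* Section 9.1.2 promises only the number not drawn. Totals by service could probably be recovered from a randomisation list stratified by service, but that is an inference.

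What remains is that the plan stratifies in order to be representative and then neither uses the stratum nor plans any check that the aim was met.

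**Conclusion.** The concern holds as a modest improvement to the two reported prevalences. It is not a flaw in the HAS–GLIM comparison; a reader might infer that the primary test is biased, and the arithmetic does not support that.

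The expected size is about 1 to 2 points on each prevalence at the planned 87% inclusion with moderate differences in acceptance. It reaches about 4.5 points if the whole loss falls in one service, and 5 to 7 points under equal quotas with markedly unequal admissions; no section states such quotas. It is zero under one fraction and equal acceptance. All of these sizes rest on assumed service shares, prevalences and acceptance rates. The missing fraction per service and the missing use of the stratum are facts of the text.

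**What to change.** - **Section 9.1.2:** state one common sampling fraction for all services, or the fraction for each. Record by service the numbers drawn, not drawn, refused and included.
- **Section 11.3:** keep McNemar. Beside the crude values, report the HAS and GLIM prevalences and their paired difference, weighted to the service mix of all eligible patients entered in the sampling system (drawn plus not drawn), with a confidence interval stratified by service.

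If inclusion turns out even, the crude and weighted values will agree and representativeness by service is shown. If not, the part of the bias that acts through service is removed.

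The cost is a few sentences and a small log by service, with no extra patients. The interval may be slightly wider if the weights turn out very uneven. Weighting by service does not correct refusal that is related to nutritional status within a service; the refusal counts at least show how much room there is for it.

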9.1.3 Patient information and consent

When all the criteria allow the inclusion of the patient, the investigator informs the patient of the purpose of the study during a visit to the room. The investigator provides the patient with all the information described in the information note ([Appendix 6](#)) and, if necessary, obtains the patient's free, informed and express oral consent. This consent will be recorded in the patient's computerised medical record.

The state of consciousness of certain patients (confusion, cognitive disorders) at the time of their admission will not allow them to receive information related to the research and the collection of consent and the information will be given to the person close to them who has been declared a trusted person ([Appendix 7](#)). At any time, if the patient's neurological or cognitive state permits, he or she will be informed of this research and asked to give express oral consent for the possible continuation of the research ([Appendix 8](#)).

In the event of a new ban on visits to hospital wards due to the health crisis, information and oral consent from the trusted support person will be given by telephone or video conference.

9.2 Inclusion visit

The inclusion visit will take place within 48 hours of the patient or relative consenting to participate in the study. The following data will be collected:

- Age, weight, height, BMI, gender (male/female) ;
- Hospitalization service ;
- Reason for hospitalisation ;
- Background;
- Reduction in food intake or absorption ;
- Inflammatory situation ;
- Biological markers (albumin, pre-albumin, CRP) if applicable;
- Nutritional data (weight evolution over the last months, theoretical needs, ingestas) ;
- Mini-Nutritional Assessment Short-Form (MNA-SF);
- Autonomy score (Katz ADL) ;
- Bioelectrical impedance data ;
- Grip force (Handgrip) ;
- Walking speed.

9.3 End of research visit

The end-of-research visit will take place when the patient is discharged from hospital or dies.

The following data will be collected:

- Duration of hospital stay (in days) ;
- Vital status (death yes/no) ;
- Autonomy score (Katz ADL).

9.4 Summary table

	Pre-inclusion	Inclusion visit	End of research visit
Informing the patient and obtaining consent			
Collection of basic data (age, weight, sex, BMI, medical history)			
Collection of service and reason for hospitalisation			
Associated diseases			
Biomarkers			
Nutritional data			
MNA-SF			
Bioelectrical impedance measurement			
Handgrip, Walking speed			
Katz ADL			
Vital status			
Length of stay in hospital			

10 Definition of evaluation criteria and measurement techniques

10.1 Prevalence of undernutrition

Undernutrition is defined according to the diagnostic methods of the HAS and GLIM:

	Phenotypic criteria			Etiological criteria	
	Weight loss (%)	Low BMI (kg/m ²)	Reduction in muscle mass	Reduction in food intake or absorption	Inflammatory situation
GLIM	> 5% in the last 6 months or > 10% beyond 6 months	< 20	Reduction assessed by a validated measurement technique*.	≤ 50% of food intake > 1 week or any reduction > 2 weeks, or any gastrointestinal conditions or symptoms impacting assimilation or absorption	Acute or certain chronic or malignant conditions
HAS	≥ 5% in 1 month or ≥ 10% in 6 months or loss ≥ 10% from usual weight before onset of disease	< 18,5	Quantified Reduction** (QR)	Same as	Same as

For the GLIM and HAS diagnostic method, the diagnosis of undernutrition is positive if an etiological criterion and a phenotypic criterion are present. The assessment of undernutrition according to GLIM will be preceded by a MNA-SF ([Appendix 4](#)). The methods for measuring the reduction in muscle mass are described in section "**7.2.4. Measurement of muscle function**".

Among patients with undernutrition, severe undernutrition is defined by :

	Moderate undernutrition	Severe undernutrition
GLIM	
 • BMI < 20 kg/m² • Weight loss of 5-10% in the last 6 months or 10-20% beyond 6 months • Mild to moderate reduction in muscle mass 	
 • BMI < 18.5 kg/m² • Weight loss of >10% in the last 6 months or >20% beyond 6 months • Severe reduction in muscle mass
HAS	
 • 17 < BMI < 18.5 kg/m² • Weight loss ≥ 5% in 1 month or ≥ 10% in 6 months or loss ≥ 10% from usual weight before onset of disease • Measurement of albumin by immuno-electrometry or immunoturbidimetry > 30 g/L and < 35 g/L. 	
 • BMI < 17 kg/m² • Weight loss ≥ 10% in 1 month or ≥ 15% in 6 months or loss ≥ 15% from usual weight before onset of disease • Measurement of albumin by immuno-electrodelemetry or immunoturbidimetry < 30 g/L

The prevalence of undernutrition is defined as the proportion of patients with moderate and/or severe undernutrition among the patients included in the study.

